2.2 SECONDARY OBJECTIVES

Among a sample of patients undergoing elective primary unilateral TKA who receive peri-articular anesthetic injections:

- 1) To compare the overall two-week levels of postoperative pain between those participants randomized to ACCs containing ropivacaine and those participants randomized to usual care without an ACC
- 2) To compare the use of opioid medications (in mean total morphine milligram equivalents) between those participants randomized to ACCs containing ropivacaine and those participants randomized to usual care without an ACC over the two-week postoperative period
- 3) To estimate the incidence of complications related to ACC placement including infection, displacement, ACC-related outpatient clinic or ED visits
- 4) To conduct exploratory analyses to identify candidate predictors of differential response to the ACC; potential interacting variables for these analyses will include demographics, baseline pain NRS scores, clinical comorbidities and secondary outcome measures.

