3.2 EXCLUSION CRITERIA

The exclusion criteria for the ACCESS study, and their rationales, are:

1. Patient declines use of ACC	1. Patient not eligible for ACC study arm
2. Surgeon decides that an ACC will not be placed for any reason	2. Patient not eligible for ACC study arm
3. Known hypersensitivity to ropivacaine or any alternative anesthetic for ACC use	3. Patient not eligible for ACC study arm
4. Hypersensitivity or inability to tolerate peri-articular injections of clonidine, epinephrine, bupivacaine and ketorolac	4. Participants in both arms of the trial are required to undergo peri-articular anesthetic injections
5. Any evidence of substance-use disorder in past year	5. Opioid use is a secondary study outcome measure
6. Non-English speaking	6. Study instruments are all in English
7. Failure to complete all baseline study instruments prior to surgery	7. No baseline measurement available for calculating change
8. Requires secondary procedure at time of TKA (e.g., removal of hardware)	8. Complex surgery may cause change in outcome measures independent of study objectives
9. Not intending to use spinal anesthesia for TKA procedure	9. Atypical surgical approach
10. Actively enrolled in KPNC chronic-pain program	10. Opioid use is a secondary study outcome measure
11. Having been prescribed long-acting opioid (e.g., Oxycontin, MS Contin) within 90 days prior to enrollment	11. Pre-surgery major opioid use may complicate measurement of post-surgery opioid use
12. Inability to tolerate any oral NSAID or acetaminophen or any short-acting opioid	12. NSAIDs, acetaminophen, and short-acting opioids are used for analgesia for all participants

These exclusion criteria are established for safety and to ensure consistency in the participant sample.

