4.2 SECONDARY OUTCOMES

Originally, the secondary outcomes included the PROMIS Global Health-10 short form and the Knee injury and Osteoarthritis Outcome Score short form (KOOS Jr). However, after further reflection among the study investigators, it was decided that these measures of symptoms and functions provided little meaningful outcome data among a sample of patients soon after knee replacement. Therefore, these measures were discarded as secondary outcome measurements.

However, the investigators decided that consumption of opioid medication in the 15 days postoperatively (as provided in the postoperative pain-and-medication diary) provided an important and meaningful secondary outcome measure for assessing the analgesic effectiveness of the ACC. The main secondary outcome measure will be the total number of 5mg oxycodone tablets (provided to all patients on discharge) consumed over the 15-day postoperative period. This change is reflected in the study schema, above.

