8.0 STATISTICAL AND DATA CONSIDERATIONS

8.1 POWER CALCULATIONS

As a noninferiority study, this trial has been powered to ensure that the lower limit of the 95% confidence interval does not cross the pre-specified noninferiority margin if the null hypothesis is rejected. We have made several conservative assumptions to ensure that the lack of a finding of noninferiority is not due to a lack of statistical power: we assumed a statistical power of 95% (very high power to increase the likelihood that the lower bound of the one-sided 95% CI will be on the null side of the noninferiority margin if usual care without an ACC is truly noninferior to use of an ACC), we have used a one-sided 95% CI of 0.025, and the variance estimate was obtained from a sample of patients similar to those intended for recruitment from the SLN Medical Center.

Special care was taken in establishing the noninferiority margin. Note that the goal of this study is not to demonstrate noninferiority in an absolute clinical sense, but to provide sufficient information to the orthopedic community in order to inform the decision regarding placement of ACC's. This insight led the PI ([name]) to conduct an e-mail poll of his colleagues, asking for their perception of the MCID that would lead to a change in practice with respect to placing ACC's. [name] received 19 replies with the following response distribution:

0.5 points: 1 (5.3%)
1.5 points: 2 (10.5%)
2.0 points: 11 (57.9%)
3.0 points: 4 (21.1%)
4.0 points: 1 (5.3%)

Mean: 2.18 points / Median: 2.0 points

Given the median MCID of 2 points, we originally chose a conservative value of 1.5 points (0.5 points below the median) for this trial, in order to maximize credibility of the results. This value was revised upward to 2.0 (see below) in version 1.1 of the protocol.

The following describes the methods and assumptions used for calculation of the necessary sample size for this study (power calculations were performed with the PASS power-analysis package (33)):

H_0 : The mean NRS pain score in the active-treatment group is less than the mean NRS pain score in the control group on the second postoperative day

H_A : The mean NRS pain score in the active-treatment group is not less than the mean NRS pain score in the control group on the second postoperative day

α : 0.025 (1-tailed) [standard practice for noninferiority trials (34)]

β : 0.02 (Power=98%)

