Secondary Aim 1: The first secondary analysis is a comparison of the mean NRS pain scores between the two treatment groups over the two-week follow-up period. We will have up to 15 measurements per individual (daily pain scores over a two-week period including baseline measurement). We are primarily interested in whether the rate of change in NRS pain score over the two-week follow-up period differs between the two treatment groups. These analyses will be conducted with linear mixed-effects models (38,39) that include terms for the effects of time, study group and the group-by-time interaction which will serve as the primary statistical test of the study hypothesis. Subjects will be included as random effects, and the within-subject correlation will be modeled appropriately. The most appropriate error structure will be chosen by comparing model fit using Akaike's Information Criterion (40). The overall difference between two total response curves will be tested with likelihood-ratio tests. The predicted

(modeled) change in the outcome over the relevant follow-up period will be obtained from each model along with the associated standard errors from which 95% confidence intervals will be constructed.

Secondary Aim 2: The mean difference in two-week postoperative opioid use (measured in total morphine equivalents) between the two treatment groups will be compared with a two-sample t-test. A secondary analysis will be conducted with a multiple linear regression model with an indicator variable for treatment group (for which the test of $\beta_1=0$ will form the primary hypothesis test) and adjustment for baseline covariates, use of opioids at baseline, and baseline NRS pain score.

Secondary Aim 3: The frequencies of complications related to ACC will be summarized with proportions and associated exact 95% confidence intervals.

Secondary Aim 4: To identify candidate predictors of differential response to the ACC, we will consider including interaction terms between the treatment indicator and demographic variables and baseline pain NRS scores in the primary linear regression analysis.

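### Secondary Aim 2 leads with an unadjusted t-test for opioid use, ranks the already planned baseline-adjusted regression below it, and words that ranking loosely

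*Combined protocol and SAP*

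**What the plan says.** Section 2.2 states the aim: "To compare the use of opioid medications (in mean total morphine milligram equivalents") between the randomized groups over two weeks. Section 4.2 gives this outcome its rank, though in a different unit: "The main secondary outcome measure will be the total number of 5mg oxycodone tablets", over 15 days.

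Section 8.2, Secondary Aim 2, names two analyses. The first is unadjusted: the mean difference "will be compared with a two-sample t-test". The second is introduced with a lower rank: "A secondary analysis will be conducted with a multiple linear regression model with an indicator variable for treatment group". Within that same sentence, a parenthesis says that the test of β₁ = 0 "will form the primary hypothesis test) and adjustment for baseline covariates, use of opioids at baseline, and baseline NRS pain score". The baseline covariates are not listed, apart from opioid use and NRS pain. No other section ranks the two analyses.

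The adjustment variables are available before allocation. Section 4.3 collects prior medication use, section 6.3 has the baseline questionnaire administered about a week before surgery, and section 6.4 places randomization on the day of surgery. Exclusion criterion 7 in section 3.2 removes patients who have not completed the baseline instruments, so missing covariates should be rare.

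**The concern.** There are two issues, both modest.

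The first is precision. Baseline opioid use and baseline pain can be expected to predict postoperative opioid use to some degree. A comparison that ignores them has a wider confidence interval than one that uses them, and the plan gives the ignoring analysis the lead although the other is already specified. The estimate at stake is the one the protocol relies on, after the day-2 pain score, to judge whether the catheter adds analgesia.

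The second is the ranking. A test described as the primary hypothesis test sits inside an analysis labelled secondary. If the two analyses disagree, the text gives each side something to cite. The unlisted covariates widen that room, because the adjusted result depends on which of them enter the model.

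**Working it through.** **The plan's own figures.** The documents give no SD, effect size or power for the opioid outcome, so there is nothing to reproduce for it directly. The stated sample size belongs to the primary outcome (section 8.1: 60 evaluable per group, margin 2.0, SD 2.64, one-sided α 0.025, power 98%):

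- SE = 2.64 × √(2/60) = 0.482.
- Power = Φ(2.0/0.482 − 1.960) = Φ(2.19) = 98.6%, in line with the stated 98%.

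I use 60 per arm below. That assumes the opioid diary is as complete as the day-2 pain score.

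**Unadjusted t-test on opioid use.** At two-sided 0.05 and 80% power, the detectable standardized difference is (1.960 + 0.842) × √(2/60) = 0.51.

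**Effect of adjustment.** R² is the share of variance in the opioid total that the baseline covariates explain. It is not in the documents, so it is assumed and shown as a range.

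- SE ratio, adjusted to unadjusted: √(1 − R²).
- Equivalent unadjusted sample per arm: 60/(1 − R²).
- Power at the standardized difference of 0.51: Φ(2.802/√(1 − R²) − 1.960).

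| Assumed R² | SE ratio | CI narrower by | Equivalent n per arm | Gain in n | Power |
|---|---|---|---|---|---|
| 0 | 1.000 | 0% | 60 | 0% | 80% |
| 0.05 | 0.975 | 2.5% | 63 | 5% | 82% |
| 0.10 | 0.949 | 5.1% | 67 | 11% | 84% |
| 0.20 | 0.894 | 10.6% | 75 | 25% | 88% |
| 0.25 | 0.866 | 13.4% | 80 | 33% | 90% |

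The SE ratios do not depend on the sample size. The formula ignores the small cost of estimating the covariate coefficients. That cost is minor for two covariates in 120 patients, but a long list of weak covariates would erode the gain at the low end.

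**Where in the range.** Section 3.2 excludes patients with "Having been prescribed long-acting opioid (e.g., Oxycontin, MS Contin) within 90 days prior to enrollment", with a substance-use disorder in the past year, or enrolled in the chronic-pain program. These exclusions narrow the spread of baseline opioid use and may weaken it as a predictor. Short-acting opioid users are not excluded as such, and baseline NRS remains available.

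**The ranking, with the wording set side by side.** In section 8.2 the primary analysis uses a similar phrase for the treatment coefficient that decides the trial. Secondary Aim 1 uses another for its group-by-time interaction, although Aim 1 is itself secondary. So the word primary sometimes points only to the key term within a model. In both of those places, however, the model is also the lead one for its aim. In Aim 2 it is not, and the phrase can therefore be read either way.

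**The case against.** A reader might infer that the plan names two competing main tests. The text does not go that far. The t-test is never called primary or main; it comes first, and the regression is labelled secondary, which is a stated order. The parenthesis follows the words about the treatment indicator, and its natural meaning is that this coefficient carries the test in that model.

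The same reader might go on to claim an inflated error rate. If either test could be reported as the main one, the chance of at least one false positive under the null would be about 6.0%, 6.5% or 7.1% at R² of 0.05, 0.10 or 0.20, instead of 5% (bivariate normal with correlation √(1 − R²) between the two statistics). That rate applies only if the choice really is free, and the secondary label argues against it. It should not be quoted as a property of the plan.

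Three further objections have weight. An unadjusted t-test in a 1:1 randomized trial is valid, and skewness alone does not rule out a comparison of means at this sample size. The adjusted result will be reported anyway. And the t-test leaves no covariate choice, whereas the regression has an open covariate list, so leading with the t-test gives some protection against selective modelling.

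All three stand as limits on severity. The third shapes the remedy: the adjusted model should lead only with its covariates fixed. None of them explains why the less precise analysis should come first when the adjusted one is already planned and its two named covariates are collected before randomization.

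**Conclusion.** The point holds as a minor one. For the leading secondary outcome the plan puts the less precise of two prespecified analyses first, and its labels leave the ranking arguable. The ranking issue rests on the text alone and needs no assumption.

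The size of the precision loss does rest on an assumption. At R² of 0.05 to 0.25, leading with the adjusted model would narrow the interval by about 2.5% to 13%, worth about 5% to 33% more patients. Quoting only the upper part of that range would overstate the case, since the exclusions may push the true value down. The t-test is not invalid, and nothing here touches the primary noninferiority conclusion.

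**What to change.** In section 8.2, Secondary Aim 2:

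- Name the linear regression adjusted for baseline opioid use and baseline NRS pain as the single main analysis. State how baseline opioid use is coded.
- List any further covariates before between-arm data are examined, or state that there are none.
- Report the adjusted mean difference with its 95% CI, preferably with heteroscedasticity-robust standard errors because opioid totals are likely to be skewed.
- Label the t-test supportive.
- Remove the conflict between the secondary and primary labels, so that one sentence says which test decides the aim.

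The cost is a few lines of SAP wording; both analyses and their data are already planned.

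Separately, sections 2.2 and 8.2 measure the outcome in morphine equivalents over two weeks, while section 4.2 counts oxycodone tablets over 15 days. Naming the main test does not settle which variable is tested, so these sections should be reconciled in the same edit.

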Inpatient hospital admission is one of the greatest contributors to the cost of the episode of care. In the last 7 years we have seen our length of stay for total knee replacement patients reduced from 3 days to less than one day. One of the major hurdles in safe patient discharge after TKA surgery is adequate pain control. The adoption of a multi-modal pain reduction strategy and, in particular, the use of the peri-articular injection has facilitated this reduction in LOS. Part of the rationale for the addition of adductor canal catheters to this pain-reduction strategy is to help improve post-operative pain and reduce LOS. In KPNC SLN, where we perform over 1,000 primary unilateral TKA surgeries each year, utilization of ACCs is variable among surgeons. Comparing length of stay in our primary TKA patients, we see the same rate of same day discharge among providers who use ACCs and those who do not. Further, a pilot study conducted at our facility in 2018 found only a very small (and clinically unimportant) difference in post-operative day 2 (when the effects of the PAI would be expected to have worn off) numerical pain score between patients with an ACC and those without. These findings are similar to a recently published randomized control study which found no difference in pain levels or opioid consumption between TKA patients with PAI alone or with PAI plus ACB (18). Our pilot study has also identified several complications associated with ACCs including leaking, dislodging, bleeding, hematoma development and prolonged neuropraxia, resulting in ED visits and phone calls to address these issues.

The entire cost of adductor canal catheters includes the pump, tubing and medication as well as the FTE provider who places them and the potential cost of ED visits or phone calls/office visits to address complications associated with the catheters. Given the cost of the catheters themselves (\$400) and the number of primary TKA surgeries performed annually in KPNC alone (> 7,000), the annual cost to our organization is estimated to be more than \$4 million.

Therefore, we propose this randomized, open-label, parallel-comparison noninferiority clinical trial to determine whether the effectiveness of these catheters justifies their cost.

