1.3 STUDY DESIGN

This is a randomized, open-label, two-arm, parallel-comparison noninferiority clinical trial of usual care with an ACC placed preoperatively compared to usual care without an ACC among adult patients undergoing elective unilateral TKA at the KPNC San Leandro Medical Center (Figure).

All patients meeting eligibility criteria will be introduced to the study by the treating orthopedist and PI, [name], at the patient's first clinic visit. If the patient expresses interest in study participation, they will be consented over the phone by the clinic Physician's Assistant (PA). Baseline data will be obtained via a telephone call with the study Research Assistant 7-10 days prior to the date of surgery. Randomization will occur in the preoperative area immediately prior to surgery. Patients will keep a daily diary of their pain levels and analgesic medication use for two weeks postoperatively and will be called by the study Research Assistant on post-op day two and day 14. A single electronic

medical record (EMR) data extraction for adverse events (focusing on emergency department and inpatient visits) will be conducted at 30 days postoperatively.

The primary outcome is the absolute pain score on post-op day two, measured on an 11-point numerical rating scale; the noninferiority margin for this comparison is set *a priori* at 2.0 points. Secondary outcomes include the total amount of opioid consumed over the two-week post-op period, the overall pain scores over the two-week post-op period, and adverse events directly attributed to the ACC.

[figure not shown]

Figure: Study Design Schema

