5.0 INTERVENTIONS

5.1.1 ACTIVE AND CONTROL CONDITIONS

Participants in the intervention arm will have implanted a bupivacaine-filled ACC immediately prior to surgery, according to usual preoperative-care practices (for the patients of those orthopedists who use the catheters). As a pragmatic trial, there will be no change in the nature of the device or the manner in which it is implanted and managed postoperatively. All other aspects of pre-surgical, operative, and post-operative care will be conducted as per usual clinical practice.

Participants in the control arm will receive identical clinical care with the exception that no ACC will be placed in their leg prior to surgery.

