7.0 ADVERSE EVENT REPORTING

7.1 CLASSIFICATION OF ADVERSE EVENTS

The ACCESS study uses the definitions of an adverse event (AE) and a serious adverse event (SAE) established by the International Conference on Harmonization (ICH) guidelines on Clinical Safety Data Management (32). These definitions are:

An adverse event (also known as “non-serious adverse event” (**NSAE**)) is any untoward medical occurrence in a patient or clinical investigation subject administered a study intervention and which does not necessarily have a causal relationship with this treatment. An adverse event can therefore be any unfavorable and unintended sign (including an abnormal laboratory finding), symptom, or disease temporally associated with the use of an intervention, whether or not considered related to the intervention. Note that adverse changes in the outcome measures of the study (e.g., pain scores) are not considered adverse events and will not be reported as such. Symptoms or other abnormalities that were present prior to a participant's randomization will not be considered adverse events (i.e., these will be treated as pre-existing conditions and not-study related); similarly, therapies (e.g., surgery) to treat a pre-existing condition are not reportable adverse events. Note that clinically meaningful *worsening* of a pre-existing condition is considered an adverse event and will be reported as such.

A Serious Adverse Event (SAE) is any untoward medical occurrence that:

- 1) results in death
- 2) is life-threatening

- 3) requires inpatient hospitalization or prolongation of existing hospitalization
- 4) results in persistent or significant disability/incapacity
- 5) is a congenital abnormality or birth defect
- 6) is an important medical event that may not result in death, be life-threatening or require inpatient hospitalization but if, based on appropriate medical judgment, it may jeopardize the patient and may require medical or surgical intervention to prevent a serious adverse event.

An Unanticipated Problem (UP) is a subset of adverse events with special reporting requirements. The definition of a UP is:

- 1) It is unanticipated (in nature, severity, and/or frequency), and
- 2) It is at least possibly related to participation in research, and
- 3) It suggests greater risk of harm to participant(s) or others than previously known or recognized (includes participants, family members, and research staff).

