7.3 REPORTING OF NON-SERIOUS ADVERSE EVENTS

All non-serious AE's will be recorded on the study AE form. All AE's will be reported in aggregate and individually to the IRB annually and to the DSM at each scheduled DSM conference call.

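### Secondary Aim 3 reports only complications attributed to the catheter and plans no comparison with the control arm, so it cannot show excess risk for events that also follow knee replacement alone

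*Combined protocol and SAP*

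**What the plan says.** The analysis of complications is one sentence in Section 8.2, Secondary Aim 3: "The frequencies of complications related to ACC will be summarized with proportions and associated exact 95% confidence intervals". It serves Objective 3 in Section 2.2: "To estimate the incidence of complications related to ACC placement including infection, displacement, ACC-related outpatient clinic or ED visits". Objectives 1 and 2 in that section are worded as comparisons of the randomized groups; Objective 3 is not. Section 1.3 lists the safety outcome as "adverse events directly attributed to the ACC".

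Other sections bear on whether a comparison could be made:

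- Section 5.1.1: "Participants in the control arm will receive identical clinical care with the exception that no ACC will be placed in their leg prior to surgery".
- Section 7.1 defines an adverse event as one that counts "whether or not considered related to the intervention".
- Section 7.3: "All non-serious AE's will be recorded on the study AE form".
- Sections 6.6 and 6.7 have the research assistant ask participants about adverse events at one and two weeks, with no restriction by arm.
- Sections 1.3 and 6.8 plan an extraction from the medical record, directed at ED and inpatient visits (1.3) and mainly at serious adverse events (6.8).

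Section 8.4 lets the safety monitor see unblinded data on request. That is monitoring, not a planned trial result.

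**The concern.** Section 1.2 says the pilot found "several complications associated with ACCs including leaking, dislodging, bleeding, hematoma development and prolonged neuropraxia". Leaking and dislodging need a catheter. Bleeding, hematoma and nerve symptoms can follow the operation itself, and so can infection, which Objective 3 names. For ED visits the documents say as much: Section 1.2 reports that pain is the leading reason for ED visits and early readmission after this operation at the sponsor's own institution.

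For these shared events, a count of attributed cases in one arm has no comparator. A control participant cannot have a catheter-related event, so the measure can only count against the catheter. If leaving the catheter out led to more pain-driven ED visits, the planned summary would not show it.

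This matters for the trial's purpose. Its title names safety, and Section 1.2 asks whether effectiveness justifies cost, counting ED visits, calls and office visits for complications as part of that cost. An incremental cost needs an incremental event count.

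**Working it through.** **Sample size available.** The plan gives no figure for complications. Section 8.1 gives 60 evaluable per group and 66 recruited per group (60 × 1.1 = 66). The stated z-test inputs (SD 2.64, margin 2.0, one-sided 0.025, power 98%) give 2 × (1.960 + 2.054)² × 2.64² / 2.0² = 56.1, so 57 per group; at 60 per group the power is 0.986. The small gap does not affect this point. I use 66 per arm.

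**Event counts.** The documents give no complication rates. All counts and rates below are assumptions.

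**1. What the planned output leaves open.** Suppose 7 of 66 catheter patients have a given event and all 7 are attributed to the catheter. The planned output is 7/66 = 10.6%. The exact (Clopper-Pearson) limits are the 2.5% quantile of Beta(7, 60) and the 97.5% quantile of Beta(8, 59): 4.4% and 20.6%. The risk difference depends on the control count, which the plan does not use. Its interval here is Newcombe's, which combines the two Wilson intervals (l, u):

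lower = d − √[(p₁ − l₁)² + (u₂ − p₂)²]; upper = d + √[(u₁ − p₁)² + (p₂ − l₂)²]

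| Catheter arm | Control arm (assumed) | Risk difference, points (95% CI) |
|---|---|---|
| 7/66 | 0/66 | +10.6 (2.9 to 20.3) |
| 7/66 | 3/66 | +6.1 (−3.6 to 16.2) |
| 7/66 | 5/66 | +3.0 (−7.4 to 13.6) |
| 7/66 | 7/66 | 0.0 (−11.1 to 11.1) |

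The planned summary is the same in all four rows.

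**2. The opposite direction.** Reverse the second row: 3/66 ED visits with a catheter, 7/66 without. The difference is −6.1 points (−16.2 to 3.6). The planned summary would show at most 3/66 = 4.5% (exact CI 0.9 to 12.7) as catheter-related and nothing from the control arm.

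**3. Precision of a comparison.** With equal rates p in both arms, the Wald half-width is 1.96 × √[2p(1 − p)/66]:

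- p = 0.05: 0.074
- p = 0.10: 0.102

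At 15% against 5% it is 1.96 × √[(0.15 × 0.85 + 0.05 × 0.95)/66] = 0.101. The interval is 10 ± 10.1 points, which just includes zero.

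**4. Power, to show what the comparison is not.** With two-sided 5% and the normal approximation, power = Φ[(Δ − 1.96 × SE₀)/SE₁], where SE₀ is pooled and SE₁ unpooled. For 10% against 5%: SE₀ = √(2 × 0.075 × 0.925/66) = 0.0459, SE₁ = √[(0.09 + 0.0475)/66] = 0.0456, and power = Φ[(0.05 − 0.0899)/0.0456] ≈ 0.19. For 80% power against a 5% control rate, the catheter rate must be about 21%.

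**5. Follow-up window.** The record extraction is at 30 days in Section 1.3, at 3 months in the synopsis and Appendix 1, and at 24 weeks in Sections 6.8 and 6.9. A count of events needs one of these.

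**The case against.** The strongest reply is that the analysis fits its objective. Objective 3 is descriptive, it concerns catheter complications, and proportions with exact intervals answer it. Displacement, which the objective names, cannot occur in a control patient, so a comparison adds nothing there. Both points stand. The concern is that the question is too narrow for the trial's purpose, not that the plan contradicts itself.

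Further replies limit what may be inferred:

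- *That catheter harm could never be separated from background.* The documents do not support this. Adverse events are recorded regardless of relatedness, so a table by arm could be made later. The gap is in the planned analysis.
- *That the one-arm proportion is wrong by the whole background rate.* This would require attribution to screen out no background events. The first table shows that extreme; nothing in the documents says attribution would be that poor.
- *That unblinded staff make the attribution.* The plan does not say who decides for Aim 3. It says only that the trial is open-label, and it describes no blinded or independent adjudication.
- *That the randomized difference would be free of bias.* It removes attribution, but patients who know they have a catheter may report more and seek care more readily.
- *That all the data are already in hand.* Extraction of all unscheduled clinic visits, and systematic questioning about nerve symptoms, are not described for either arm.

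Tables by arm may also be specified in the separate safety monitoring plan, which is not available here. They would serve monitoring, and Section 8.2 would still lack the estimate.

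**Conclusion.** The point holds for events possible in either arm. For infection, bleeding or hematoma, nerve symptoms and ED visits, Aim 3 as written cannot show excess risk in either direction and depends on open-label attribution. For displacement and leaking the plan is adequate.

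The size cannot be fixed from the documents. Under the assumed counts, one planned result (10.6%) fits differences from 0 to 10.6 points. A reader might infer that adding the control arm would be enough to show a large excess. It would not, short of a very large one: a tripling from 5% to 15% would still just include zero. The gain is an estimate with a comparator and an honest interval, not a safety test. The primary analysis is unaffected. The change is worth making because it is cheap and serves the trial's stated purpose.

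**What to change.** Amend Secondary Aim 3 in Section 8.2, and align Objective 3 and the outcome list in Section 1.3:

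- Tabulate by randomized arm, regardless of attribution, the recorded adverse events that can occur in either arm (infection, bleeding or hematoma, nerve symptoms) and the ED and inpatient visits from the record extraction.
- Give risk differences with 95% CIs suited to sparse counts, such as Newcombe or exact, and label them descriptive.
- Use one follow-up window for both arms, after reconciling the 30-day, 3-month and 24-week statements.
- Include unscheduled clinic visits only if they are extracted the same way in both arms.
- Keep one-arm exact intervals for device-only events (displacement, leaking).
- State when reporting that open-label reporting and care-seeking may affect the comparison.

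The cost is a little more analysis, some added extraction if clinic visits are included, and wide intervals. No added participants are needed.
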